CONFIDENTIAL

This document is confidential. Do not disclose or use except as authorized.

or CT. If the CT scan suggests an inadequate ablation margin of less than 5-10 mm at any portion of the tumor surface, additional ablations will be applied to the under-treated areas (Pathway 2), if deemed safe and appropriate based on standard clinical practice. Then, AP-PET-2 will be repeated (research scan #2). Not more than two AP-PET scans will be performed during the entire procedure. The AP-PET scan(s), illustrated schematically below, constitute the only research component of the protocol.

Arm 2: Arm 2 will not include the option of AP-PET 2 (research scan #2) due to the longer half-life of FDG.

The devascularized ablation zone contains trapped high tumor FDG activity and low ablation margin FDG activity, whereas normal liver is perfused with high activity ¹³N-ammonia. The relatively photopenic ring around the tumor confirms the presence of an adequate ablation margin.

For patients with FDG-avid tumors, visibility rates of the entire ablation margin using AP-PET-1 will be compared to the visibility rates of the entire ablation margin using the intra-procedural CECT scan. Visibility rates using AP-PET-1 will also be compared to the visibility rates using the intra-procedural CECT scan fused to FDG PET (FDG PET/CECT). The concordance rates of the final intra-procedural AP-PET (research scan #1 or #2) with gold standard 24-hour post-procedure MRI or CT will be determined.

For those patients with non-FDG-avid tumors, retrospective software fusion of AP-PET-1 with pre-procedural MRI or CT will be used to assess visibility rates of the ablation margin and will be compared with visibility rates of the ablation margin using retrospective fusion of the intra-procedural CECT and pre-procedural MRI or CT. Similarly, in patients with non-FDG-avid tumors the concordance rate of final intra-procedural AP-PET (research scan #1 or #2) fused to pre-procedural MRI or CT, with gold standard 24-hour post-procedure MRI or CT will be determined. The analysis of AP-PET utility in patients with non-FDG-avid tumors is a secondary objective of this study, but is nevertheless of interest, as AP-PET may prove valuable in these patients who cannot receive IV contrast or

CONFIDENTIAL

This document is confidential. Do not disclose or use except as authorized.

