1.2 Primary Objectives

Arm 2: The primary and secondary objectives are identical for Arms 1 & 2 of the study (except that in Arm 2, no research scan #2 will be performed).

- 1. For FDG-avid tumors, compare the rates of complete, circumferential ablation margin visibility during FDG PET/CT-guided liver ablations using two imaging techniques: intra-procedural AP-PET-1 (research scan #1) and intra-procedural CECT. Discordance rates for complete ablation margin visibility between the two imaging techniques will be calculated.
- 2. For FDG-avid tumors, compare the rates of complete, circumferential ablation margin visibility during FDG PET/CT-guided liver ablations using two imaging techniques: intra-procedural AP-PET-1 and intra-procedural CECT fused with FDG PET (FDG PET/CECT). Discordance rates for complete ablation margin visibility between the two imaging techniques will be calculated.
- 3. In assessing adequacy of the ablation margin for FDG-avid tumors, the concordance rates of final intra-procedural AP-PET (research scan #1 or #2) with gold standard 24-hour post-procedure MRI or CT will be determined. (Includes patients with renal insufficiency who cannot receive intra-procedural iodinated IV contrast.)
- 4. For non-FDG-avid tumors, compare the rates of complete, circumferential ablation margin visibility during FDG PET/CT-guided liver ablations using two imaging techniques: 1) intra-procedural AP-PET-1 fused to pre-procedural MRI or CT and 2) intra-procedural CECT fused to pre-procedural MRI or CT. Discordance rates for complete ablation margin visibility between the two imaging techniques will be calculated.
- 5. In assessing adequacy of the ablation margin for non-FDG-avid tumors, the concordance rate of final intra-procedural AP-PET (research scan #1 or #2) fused to pre-procedural MRI or CT with gold standard 24-hour post-procedure MRI or CT will be determined. (Includes patients with renal insufficiency who cannot receive intra-

CONFIDENTIAL

This document is confidential. Do not disclose or use except as authorized.

procedural iodinated IV contrast.)

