- **This study will assess the rates of complete ablation margin visibility using AP-PET alone in comparison to CECT alone or fused PET/CECT. This study will assess the concordance of final intraoperative assessment of tumor ablation results using AP-PET with results observed on gold standard 24-hour contrast-enhanced MRI or CT.**
- **Patients may benefit from participation in this study if AP-PET can be used to identify an inadequate ablation margin not evident on CECT or in patients who cannot undergo CECT and are scanned without contrast. In such cases, additional overlapping ablations may be performed during the same procedure and thus increase the chance of technical success (complete tumor ablation rate) and technique effectiveness (low local recurrence rate). The safety of any additional ablation applications would be based on routine intraoperative CT scans per standard practice.**

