14. STATISTICAL CONSIDERATIONS

14.1 Study Design/Endpoints

Arm 2: Study design/endpoints are identical for Arms 1 & 2.

In this study of patients with liver lesions, it is expected that roughly two-thirds of patients will have FDG-avid tumors, one-third of patients will have non FDG-avid tumors, and although it is possible for a patient to have both types of tumor, that is considered rare. For sample size and power considerations we therefore conservatively assume that patients will have one type of tumor or the other and therefore target a sample size of 100 patients per arm, allowing for the potential for renal insufficiency in up to 25% of all patients (described in more detail below). Also, as the techniques focus on analysis by tumor and it is estimated that 70% of patients will have only a single lesion, the sample size considerations will focus on enrolling *patients* rather than *tumors*. Multiple tumors per patient, when they occur, will be treated and assessed in the statistical analysis, with appropriate adjustment for clustering of tumors within a patient to account for correlation of responses within a patient. Sample size considerations, however, focus on enrollment of patients. The study design and endpoints are identical for Arm 1 and Arm 2.

Primary Objectives:

1. Among FDG-avid liver tumors, comparison of imaging techniques will be done on paired tumor samples using McNemar's test, focusing on discordant pairs (AP-PET-1 adequate/CECT inadequate and AP-PET-1 inadequate/CECT adequate). For these comparisons it is expected that the rate of discordance will be high (near 60% of all pairs) and that differential in discordance will be large (difference between discordant pairs on the order of 50% or higher). In addition to comparing discordant pairs, there is interest in being able to precisely estimate the visibility rates under each imaging modality. With 50 paired samples in the FDG-avid liver tumor ablation group in each arm, visibility of the entire ablation margin can be estimated with a 95% binomial confidence interval that should be no wider than 24 percentage points (+/- 12%) in the expected range of visibility of each modality (80% for AP-PET and 20% for CECT). This sample size will provide greater than 90% power for McNemar's test using a 5% type I error given the assumptions above about discordance.

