Since both imaging modalities are required for McNemar's test and the rate of renal insufficiency that would preclude a paired CECT scan is estimated to be roughly 25%, inflation for loss due to patients with renal insufficiency implies that the FDG-avid tumor target sample size for this trial is 67 patients per arm ($=50/0.75$). The trial will be monitored closely for

CONFIDENTIAL

This document is confidential. Do not disclose or use except as authorized.

potential early closure if the rate of renal insufficiency is lower than 25% or potential extension of accrual if the yield of paired samples is lower than 75%.

2. With at least 50 evaluations in the FDG-avid liver tumor treated group per arm, the visibility rates for AP-PET-1 and intra-procedural PET/CECT will be estimated with an accuracy of +/- 12% using 95% confidence intervals for binomial proportions. With this sample size, if the observed visibility rate is near 90%, the 95% confidence interval width is expected to be shorter than 19 percentage points.

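### Primary Objective 2 is a paired comparison of AP-PET-1 with fused FDG PET/CECT, but section 14.1 plans only one confidence interval per modality and none for the paired difference

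*Combined protocol and SAP*

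**What the plan says.** Section 1.2, item 2, sets a comparison in FDG-avid tumours between AP-PET-1 and intra-procedural CECT fused with FDG PET. It adds: "Discordance rates for complete ablation margin visibility between the two imaging techniques will be calculated". The abstract (1.1) repeats the comparison, and section 2.3 says the study will assess "rates of complete ablation margin visibility using AP-PET alone in comparison to CECT alone or fused PET/CECT".

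The analysis for this objective is in section 14.1, item 2. With at least 50 evaluations per arm, "the visibility rates for AP-PET-1 and intra-procedural PET/CECT will be estimated with an accuracy of +/- 12% using 95% confidence intervals for binomial proportions". It adds that the interval should be narrower than 19 points if the observed rate is near 90%. It mentions no paired difference, no interval or test for one, and no assumed discordance.

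Item 1 is different. There, "comparison of imaging techniques will be done on paired tumor samples" with McNemar's test, but its discordant pairs are defined as AP-PET-1 against CECT alone. Item 4 also uses McNemar's test, for non-FDG-avid tumours. Sections 14.4 and 14.5 only refer back to 14.1. The opening of 14.1 promises that multiple tumours will be analysed "with appropriate adjustment for clustering of tumors within a patient", without naming a method.

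**The concern.** The objective is a comparison, but the planned analysis describes each technique separately. The documents do not say in so many words that both reads are on the same tumours. It follows from both techniques being applied in the same procedure, and from the discordance rates, which need paired reads. For paired proportions the uncertainty of the difference depends on the discordant pairs as well as on the two rates, so two one-sample intervals cannot supply it.

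This is the only objective that sets AP-PET-1 against fused PET/CECT. Section 2.3 presents the fused scan as the other way to use the tumour's retained FDG signal, and argues that AP-PET avoids its misregistration problem. The large contrast expected in item 1 (80% against 20%) is for CECT alone, and no expected rate or discordance is given for the fused scan. One therefore cannot assume that the gap will be so wide that separate intervals settle the matter.

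**Working it through.** **1. The plan's own figures (n = 50, 14.1 items 1 and 2).** Exact (Clopper-Pearson) 95% intervals:

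| Visible | Interval | Width (points) |
|---|---|---|
| 45/50 (90%) | 78.2-96.7% | 18.5 |
| 40/50 (80%) | 66.3-90.0% | 23.7 |
| 35/50 (70%) | 55.4-82.1% | 26.7 |

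The 18.5 reproduces the stated figure of under 19. The 23.7 (half-width 11.8) reproduces +/- 12%, and the width at 20% is the same by symmetry. At 70% the half-width is 13.4 exact, or 12.7 by the normal approximation, so +/- 12% no longer holds. Item 1 ties its +/- 12% to rates of 80% and 20%; item 2 drops that condition.

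**2. An illustration for the comparison.** The documents give no discordance for this pair, so these counts are assumed: AP-PET-1 visible in 45/50, fused PET/CECT in 37/50, one tumour per patient. The difference is 0.90 - 0.74 = 0.16.

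Planned output: 78-97% and 60-85%. They overlap from 78% to 85%, whatever the discordant pairs are.

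**3. Interval for the paired difference.** Newcombe's method, no continuity correction. Let *b* be the tumours visible on AP-PET-1 only, *c* on PET/CECT only, *a* on both and *d* on neither.

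- Wilson limits: 45/50 gives l1 = 0.786, u1 = 0.957; 37/50 gives l2 = 0.604, u2 = 0.841.
- phi = (ad - bc) / sqrt(45 x 5 x 37 x 13) = (ad - bc) / 329.0
- Lower = 0.16 - sqrt[(0.90 - l1)^2 - 2 phi (0.90 - l1)(u2 - 0.74) + (u2 - 0.74)^2]
- Upper = 0.16 + sqrt[(0.74 - l2)^2 - 2 phi (0.74 - l2)(u1 - 0.90) + (u1 - 0.90)^2]

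For split 8/0: a = 37, d = 5, phi = 185/329.0 = 0.56. Lower = 0.16 - sqrt(0.01290 - 0.01293 + 0.01026) = 0.059. Upper = 0.274.

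| b/c | a, d | phi | 95% interval (points) |
|---|---|---|---|
| 8/0 | 37, 5 | 0.56 | 5.9 to 27.4 |
| 9/1 | 36, 4 | 0.41 | 4.3 to 28.4 |
| 10/2 | 35, 3 | 0.26 | 2.9 to 29.3 |
| 11/3 | 34, 2 | 0.11 | 1.6 to 30.1 |

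These are all the splits with non-negative association. Each excludes zero although the marginal intervals overlap. The width runs from 21.5 points (27.4 - 5.9) to 28.5 points (30.1 - 1.6) with the two planned intervals unchanged.

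**4. What the promised discordance rates add.** If both rates and the total discordance are reported on the same pairs, the table is fixed. For rates of 90% and 74% with 28% discordance at n = 50: b - c = 0.16 x 50 = 8 and b + c = 0.28 x 50 = 14, so b = 11 and c = 3.

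**The case against.** The strongest reply is that section 1.2 already promises discordance rates for this pair. Step 4 shows that, with both rates on the same tumours, even the total discordance recovers the 2x2 table. This stands. A reader might infer that the planned outputs make different paired results indistinguishable, or that pairing is ignored. The documents do not support that. The information would be available, but the interval and the method for it are not specified, and a rebuilt table would not carry the clustering adjustment.

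A reader might also infer that the same two marginal intervals could hide opposite conclusions. With these margins the only split whose Newcombe interval includes zero is 13/5 (-1 to 32 points). It needs negative association (phi = -0.20) and no tumour invisible on both reads, which is implausible when both reads use the same FDG tumour signal. That contrast should not be used. The conclusion near the boundary does depend on the method: at 11/3 the exact McNemar p-value is 0.057, although the Newcombe interval excludes zero. This is a reason to name the method beforehand.

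It can also be said that item 2 deliberately estimates and does not test. That is legitimate, and neither a test nor a power claim is required here. But if the aim is estimation, the quantity to estimate in a comparative objective is the difference. Finally, the stated precision figures are correct, and the +/- 12% wording is minor because item 1 gives the condition just before.

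**Conclusion.** The point holds as an omission: a primary comparative objective has no planned interval for its paired difference, while items 1 and 4 name a paired analysis for theirs. In the illustration, overlapping intervals of 78-97% and 60-85% go with a 16-point difference whose paired interval excludes zero (6 to 27 points at split 8/0, 2 to 30 at 11/3). Reading the planned intervals side by side would understate the evidence.

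The size rests on assumed counts, non-negative association, Newcombe's method and one tumour per patient; clustering is ignored in the calculation. The documents do not support reading this as an arithmetic error, a loss of the paired data, or a shortfall in power. It is a cheap improvement to the plan.

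**What to change.** In section 14.1, item 2:

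- Make the main analysis the paired difference in complete-margin visibility, AP-PET-1 minus FDG PET/CECT, on tumours with both reads.
- Give it a 95% confidence interval by one method named in advance, consistent with the clustering adjustment that 14.1 already promises. Examples are a patient-level bootstrap or GEE with patient as the cluster if all tumours are used, or Newcombe's paired interval if one tumour per patient is analysed.
- Report both discordant cells.
- Keep the per-modality intervals as supporting estimates.
- Minor: say that +/- 12% applies at visibility of about 80% or higher, or 20% or lower.

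The cost is a short paragraph and a little extra analysis. No new patients, scans or reads are needed.

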The purpose of this study is to evaluate a novel imaging technique for intra-procedural assessment, also known as monitoring, of image-guided percutaneous liver tumor microwave or cryoablation (thermal ablation) procedures. Monitoring assures that the tumor is being ablated completely (and nearby critical structures left unharmed) by allowing the interventionalist to view ablative changes and make intra-procedural adjustments to the location of the ablation applicators, the number of overlapping ablation treatments, or the duration of ablation applications. As a result, improved monitoring has the potential to improve patient outcomes. We will assess a novel method for monitoring ¹⁸F-fluorodeoxyglucose (FDG) Positron Emission Tomography/Computed Tomography (PET/CT)-guided liver tumor ablations: intra-procedural ¹³N-ammonia perfusion PET (AP-PET). N-13 ammonia is FDA-approved for cardiac perfusion imaging, but will be used in this study for the off-label indication of imaging perfusion of the liver. The standard dose and IV route of administration will be employed. We will compare this method of assessing immediate technical success of ablation procedures to standard assessments using intra-procedural contrast-enhanced CT (CECT). We will also compare final intra-procedural ammonia perfusion PET to gold standard 24-hour magnetic resonance imaging (MRI) or CT for predicting longer term technique effectiveness as demonstrated on routine MRI (or if MRI is not possible, on CT) obtained at a minimum of three to 12 months after the procedure.

This study will evaluate if AP-PET can be used intra-procedurally during FDG PET/CT-guided ablation procedures to identify regions of the ablation zone that do not adequately treat the tumor. The ablation zone is the volume of tissue destroyed by the ablation treatment. Adequate ablation treatment of tumor is generally defined by a minimum ablation margin of 5-10 mm. The ablation margin refers to the rim of normal tissue beyond the tumor included within the ablation zone in order to assure that even microscopic tumor

CONFIDENTIAL

This document is confidential. Do not disclose or use except as authorized.

extensions beyond the visible tumor are fully destroyed.

The ablation zone includes the ablated tumor and a cuff of ablated surrounding normal liver (ablation margin).

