3. In patients with FDG-avid liver tumors, the goal of this objective is to assess the proportion of cases confirmed to have adequate ablation margins using 24-hour MRI or CT as the gold standard among those identified as nominally adequate at the time of final intra-procedural imaging. Note that for this objective, patients do not have to receive intra-procedural iodinated IV contrast, hence the reduction in sample size due to renal insufficiency does not apply to this objective. It is expected that nearly 95% of cases will be identified as nominally adequate by all available post-ablation intra-procedural imaging data (i.e. standard-of-care imaging plus AP-PET). With 75 cases per arm, this translates to roughly 71 nominally adequate cases. Among these cases, the ablation margin adequacy rates based on 24-hour MRI or CT will be estimated with 95% binomial confidence intervals and it is expected that the adequacy rates for all available post-ablation intra-procedural imaging will be high, in the range of 90% or higher. With the sample size stated above, the 95% confidence intervals to confirm adequate ablation after 24 hours will be no wider than 16 percentage points (+/- 8%). It is also of interest to confirm that margins that were deemed inadequate on AP-PET alone were confirmed inadequate based on 24-hour MRI or CT but this objective is largely exploratory since the sample size for cases labeled inadequate after AP-PET is expected to be very low, only 5% of the total cases. Finally, it is of interest to assess agreement of final intra-procedural AP-PET with 24-hour MRI or CT. Concordance rates are unknown but are estimated to be in the range of 50 to 80%. With 75 cases per arm, the 95% confidence intervals on the concordance rates are expected to be no wider than 24 percentage points (+/- 12%) assuming, conservatively, that the true concordance rate is near 50%.

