5. In patients with non FDG-avid liver tumors, the goal of this objective is to assess the proportion of cases confirmed to have adequate ablation margins using 24-hour MRI or CT as the gold standard among those identified as nominally adequate at the time of final intra-procedural imaging. Patients evaluated for this objective do not have to receive intra-procedural iodinated IV contrast. It is expected that nearly 95% of cases will be identified as nominally adequate by all available post-ablation intra-procedural imaging data (i.e. standard-of-care imaging plus AP-PET). With 33 cases per arm, this translates to roughly 31 nominally adequate cases. Among these cases, the ablation margin adequacy rates based on 24-hour MRI or CT will be estimated with 95% binomial confidence intervals and it is expected that the adequacy rates for all available post-ablation intra-procedural imaging will be high, in the range of 90% or higher. With the sample size stated above, the 95% confidence intervals to confirm adequate ablation after 24 hours will be no wider than 24 percentage points ($\pm 12\%$). It is also of interest to confirm that margins that were deemed inadequate on AP-PET fused to pre-procedural MRI or CT were confirmed inadequate based on 24-hour MRI or CT but this objective is largely exploratory since the sample size for cases labeled inadequate after AP-PET fused to pre-procedural MRI or CT is expected to be very low, only 5% of the total cases. Finally, it is of interest to assess agreement of final intraprocedural AP/FDG PET fused to pre-procedural MRI or CT with 24-hour MRI or CT. Concordance rates are unknown but are estimated to be in the range of 50 to 80%. With 33 cases per arm, the 95% confidence intervals on the concordance rates are expected to be no wider than 36 percentage points ($\pm 18\%$) assuming, conservatively, that the true concordance rate is near 50%.

Secondary Objectives:

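### Objectives 3 and 5 do not name or size the share of margins inadequate at 24 hours that AP-PET called inadequate; adding it from data already collected is a cheap improvement

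*Combined protocol and SAP*

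**What the plan says.** Section 1.1 gives the aim as testing whether AP-PET can "identify regions of the ablation zone that do not adequately treat the tumor".

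Section 14.1, Primary Objective 3 (FDG-avid tumours), plans three things:

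- **Confirmation rate.** The main goal is the "proportion of cases confirmed to have adequate ablation margins using 24-hour MRI or CT as the gold standard among those identified as nominally adequate". The plan expects that "nearly 95% of cases will be identified as nominally adequate by all available post-ablation intra-procedural imaging data", where that imaging is standard of care plus AP-PET. It then states: "With 75 cases per arm, this translates to roughly 71 nominally adequate cases". The confirmed share is expected to be high, "will be high, in the range of 90% or higher".
- **Check of inadequate calls.** Whether margins called inadequate on AP-PET were also inadequate at 24 hours. This is labelled largely exploratory because the "sample size for cases labeled inadequate after AP-PET is expected to be very low, only 5% of the total cases".
- **Agreement.** Concordance of final AP-PET with 24-hour MRI or CT over all 75 cases, assumed to be 50–80%. Section 1.2 words Objectives 3 and 5 as concordance rates.

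Primary Objective 5 (non-FDG-avid tumours) repeats this with 33 cases, about 31 of them nominally adequate, again conditioning on "among those identified as nominally adequate at the time of final intra-procedural imaging".

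Neither sensitivity nor specificity against 24-hour imaging is named anywhere in section 14.1.

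**The concern.** A monitoring test meant to reveal under-treatment is judged by how many under-treated tumours it finds. That quantity conditions on the 24-hour result. The confirmation rate and the exploratory check both condition on the intra-procedural call. Concordance conditions on neither and pools correct adequate calls with correct inadequate calls. When adequate margins predominate, both the confirmation rate and concordance are driven by the adequate group.

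The risk is one of interpretation. A report that about 90% of adequate calls were confirmed, or that agreement was about 90%, would read as support for AP-PET as a detector of under-treatment, although a test that missed most inadequate margins could produce the same figures. If sensitivity is not specified in advance, whether it is reported becomes optional.

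**Working it through.** **Reproducing the plan's figures.** 75 × 0.95 = 71.25 and 33 × 0.95 = 31.35, matching the stated 71 and 31. Exact (Clopper-Pearson) 95% interval widths also fall within the stated maxima:

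| Quantity | Exact width (points) | Plan's maximum |
|---|---|---|
| n = 71 at 90% | 15.2–15.3 | 16 |
| n = 75 at 50% | 23.6 | 24 |
| n = 31 at 90% | 23.7–24.0 | 24 |
| n = 33 at 50% | 35.7 | 36 |

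The arithmetic for the planned quantities is therefore sound. The question is what they leave out.

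**Illustrative ceiling on sensitivity.** Let c be the share called inadequate (5%, section 14.1 item 3), q the share of adequate calls confirmed (90% or more, same item), and PPV the share of inadequate calls that are right. Then

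sensitivity = c × PPV / [c × PPV + (1 − c)(1 − q)].

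PPV = 1 gives the largest possible value. The calculation also assumes that AP-PET's call equals the combined-imaging call, because the plan gives its 95% and 90% figures for combined imaging.

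| q | Ceiling | Inadequate at 24 h, of 75 | Of 33 |
|---|---|---|---|
| 90% | 0.05/(0.05 + 0.095) = 34.5% | 10.9 | 4.8 |
| 95% | 0.05/(0.05 + 0.0475) = 51.3% | 7.3 | 3.2 |
| 99% | 0.05/(0.05 + 0.0095) = 84.0% | 4.5 | 2.0 |

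The ceiling does not depend on the number of cases, so it is the same for Objective 5. It is also unaffected by item 1 of section 14.1 targeting 67 FDG-avid patients per arm while item 3 uses 75 cases.

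**Can the planned numbers separate AP-PET from a test that detects nothing?** At q = 90% and PPV = 1, the share of margins adequate at 24 hours is 1 − 0.145 = 85.5%. A rule calling every tumour adequate would therefore be confirmed, and concordant, in 85.5%.

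- Confirmation rate: 64/71 = 90.1%, exact 95% CI 80.7% to 95.9%.
- Concordance: at most 0.95 × 0.90 + 0.05 = 90.5%, about 68/75, exact 95% CI 81.7% to 96.2%.

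Both intervals contain 85.5%.

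**Consistency of the plan's inputs.** If the two calls are the same, agreement is at least 0.95 × 0.90 = 85.5% even if every inadequate call is wrong. The plan assumes 50–80% for AP-PET. Taking 80% with 5% called inadequate and PPV = 1 implies that only 1 − 0.20/0.95 = 78.9% of adequate calls are confirmed, and a sensitivity ceiling of 0.05/(0.05 + 0.20) = 20.0%. At 50% concordance the ceiling is 0.05/(0.05 + 0.50) = 9.1%. So either AP-PET's call differs from the combined call, or the assumptions conflict.

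**Precision of a sensitivity estimate.** With about 11 cases inadequate at 24 hours, 4/11 = 36.4% has an exact 95% CI of 10.9% to 69.2%.

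**The case against.** The strongest reply is that the plan does not look only at the intra-procedural call. Concordance uses all 75 (or 33) cases, is how section 1.2 words both objectives, and needs the same cross-classification from which sensitivity is computed. That stands: the data will exist, and the gap is that sensitivity is neither named nor sized. It does not make concordance a substitute, as the 85.5% comparison shows.

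A reader might infer that the plan's own figures cap AP-PET's sensitivity at about 35%. The documents do not support that:

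- The confirmed share is given as 90% or higher, so 35% is the lowest ceiling in the stated range, not a cap.
- The 95% and 90% rates belong to all imaging combined. Only the 5% is attributed to AP-PET, and the 50–80% concordance assumption suggests the two calls may differ.
- The rates describe the final assessment. Under Pathway 2 in section 1.1, areas judged inadequate on CT may be re-ablated first, so tumours found and re-treated leave the inadequate group. The figures therefore do not bound detection by AP-PET-1.

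A reader might also infer that the inadequate group is about three times what the plan assumes. The plan gives 5% as the share called inadequate and never states how many margins will be inadequate at 24 hours, so there is no assumed count to compare with.

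It is also fair that Objectives 1, 2 and 4 concern visibility, that the power statements belong to Objectives 1 and 4, and that a sensitivity estimate here would be very imprecise. That makes this a reporting improvement rather than a design fault.

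**Conclusion.** The point holds as a cheap improvement. Objectives 3 and 5 plan a confirmation rate, an exploratory check of inadequate calls and a concordance rate. None gives the share of margins inadequate at 24 hours that AP-PET called inadequate, although section 1.1 makes finding under-treatment the aim.

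The size can only be illustrated: ceilings of about 35%, 51% and 84% at 90%, 95% and 99% confirmed. These rest on AP-PET matching the combined call, 5% called inadequate and every inadequate call being right. They show that a favourable confirmation or concordance rate does not establish detection. They do not show that AP-PET's sensitivity is low.

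**What to change.** In section 14.1, items 3 and 5:

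1. Report the full two-by-two table of the final AP-PET-alone call (fused to pre-procedural MRI or CT for non-FDG-avid tumours) against 24-hour MRI or CT.
2. Report sensitivity and specificity beside the confirmation and concordance rates, with 95% intervals. Use exact intervals, or clustering-adjusted ones where patients contribute several tumours, in line with the adjustment already promised in section 14.1.
3. In Arm 2, report cases re-ablated after the only AP-PET scan separately. Section 1.1 allows no second scan in that arm, so the scan predates the margin judged at 24 hours.
4. State the expected precision: about 11 FDG-avid and 5 non-FDG-avid margins inadequate at 24 hours per arm if 90% of adequate calls are confirmed, with 4/11 (11% to 69%) as an example.
5. Reconcile the 50–80% concordance assumption with the 95% and 90% figures, or say that AP-PET's call is expected to differ from the combined call.

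The cost is analysis wording, the extra tables and the separate handling of re-ablated Arm 2 cases. No new scan or patient is needed. The downside is a wide sensitivity interval and a headline that may look less favourable.
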